7.5. PHARMACOKINETIC (PK) POPULATION

The PK population is defined as all subjects in the Safety population for whom the primary PK data are considered sufficient and interpretable.

7.6. WINDOWING VISITS

Although there is a visit window from 2 to 4 days around the expected visit date, nominal visits will be used for the per-visit analyses. Therefore, no windowing of visits by study day will be done for data obtained at the scheduled visits. For subjects who withdraw from the study prematurely, if the early termination visit falls into the window of a scheduled visit as defined in the protocol, the early termination visit is also summarized for that scheduled visit, unless the scheduled visit already took place.

8. STUDY SUBJECTS

8.1. SUBJECTS SCREENED

The number of subjects screened will be presented.

8.2. STUDY ANALYSIS POPULATIONS

The number and percent of subjects in each study analysis population (i.e., ITT, PP, Safety and PK) will be presented for the Screened population.

8.3. Protocol Deviations

Protocol deviations as obtained from a clinical trial management system (CTMS) will be assessed throughout the study. All identified deviations will be reported in the CTMS. Protocol deviations from the CTMS will be coded to severity categories ("minor", "important" and "priority") and provided as part of the CTMS transfer to Biostatistics. Protocol deviations will be summarized for the ITT population. A listing of protocol deviations by subject will be presented in the data listings.

Document: T:\Shire\Teduglutide\XXA39799\Biostatistics\Documentation\SAP\SHP633-302 SAP Final

1.0_17Apr2019.docx

Version Number: Final 1.0
Version Date: 17Apr2019

Reference: CS WI BS005

Template No: CS TP BS016 Revision 4

Effective Date: 01Apr2016

Author:

Copyright © IQVIA. All rights reserved.

8.4. DISPOSITION OF SUBJECTS

For the ITT, PP, PK and Safety populations, study enrollment as well as treatment and study completion status will be summarized. The reason for discontinuing treatment and/or study early will also be presented.

9. Demographic and Other Baseline Characteristics

9.1. Analysis of Demographic and Other Baseline Characteristics

The baseline and demographic characteristics will be summarized with descriptive statistics defined in Section 6.1 for the ITT and Safety populations. Demographic and baseline characteristics to be presented include:

- Age at informed consent date in years for the cohort of children 1-15 years of age. Age in years will be rounded to 1 decimal place for reporting.
- Chronological (actual) age at informed consent date in months for the infant cohort. Chronological age in months will be rounded to 1 decimal place for reporting.
- Corrected gestational age at informed consent date in months for the infant cohort. Corrected gestational age in months will be rounded to 1 decimal place for reporting.
- Sex
- Race
- Ethnicity
- · Height or length for age Z-score at Baseline
- Weight for age Z-score at Baseline
- Head Circumference for age Z-score at Baseline (only for subjects who are <= 36 months of age)
- BMI for age Z-score at Baseline only for children 2-15 years of age
- Weight for length Z-score at Baseline only for the infant cohort

BMI, Z-score of weight, height or length, BMI and head circumference for age as well as weight for length Z-score will be calculated based on the method described in Section 13.4. Z-scores will be rounded and presented to 2 decimal places.

The following Short Bowel Syndrome History information collected at the Screening visit will be summarized with descriptive statistics defined in Section 6.1 for the ITT and Safety populations:

Document: T:\Shire\Teduglutide\XXA39799\Biostatistics\Documentation\SAP\SHP633-302 SAP Final

1.0 17Apr2019.docx

Version Number: Final 1.0 Version Date: 17Apr2019

Reference: CS WI BS005

Template No: CS_TP_BS016 Revision 4

Effective Date: 01Apr2016

Author:

Copyright © IQVIA. All rights reserved.

- Duration of SBS
- Primary reason for the diagnosis of SBS (necrotizing enterocolitis, midgut volvulus, intestinal atresia, gastroschisis, trauma, cancer, crohn's disease, long-segment hirschprung disease, other)
- Secondary reason for the diagnosis of SBS (Y/N), secondary reason (necrotizing enterocolitis, midgut volvulus, intestinal atresia, gastroschisis, trauma, cancer, crohn's disease, long-segment hirschprung disease, other)
- stoma (Y/N), stoma type (jejunostomy, ileostromy, colostomy, other)
- Remaining colon (Y/N), estimated percent of colon remaining, and colon in continuity (Y/N)
- Colonoscopy in the last 12 months (Y/N/NA)
- Total estimated remaining small intestinal length (cm)
- Presence of the distal/terminal ileum (Y/N) and ileocecal valve (Y/N)
- Method to determine remaining anatomy length (surgery, radiology, other)

For children 1-15 years of age, duration of SBS in years will be calculated as (Date of informed consent form signed – Date of diagnosis of SBS +1) / 365.25 and rounded to 1 decimal place for reporting.

For infants, duration of SBS in months will be calculated as (Date of informed consent form signed – Date of diagnosis of SBS +1) / (365.25/12) and rounded to 1 decimal place for reporting.

The following Parenteral Nutrition/Intravenous History and Enteral Nutrition (EN) History information collected at the Baseline visit will be summarized with descriptive statistics defined in Section 6.1 for the ITT and Safety populations:

- Years or months since start of PN/IV dependency
- Current use of EN (Y/N), reason not taking EN (following a regular diet, other)
- Years or months since start of EN dependency

For children 1-15 years of age, years since start of PN/IV dependency will be calculated as (Date of informed consent form signed – Start date of PN/IV dependency +1)/365.25.

For infants 4-12 months corrected gestational age, months since start of PN/IV dependency will be calculated as (Date of informed consent form signed – Start date of PN/IV dependency +1)/ (365.25/12).

Years and months since start of EN dependency will be calculated in a similar manner but using the start date of EN dependency. Both these durations will be rounded to 1 decimal place for reporting.

The following Parenteral Nutrition/Intravenous History information collected at baseline will be summarized in the by-visit efficacy tables and listed:

Document: T:\Shire\Teduglutide\XXA39799\Biostatistics\Documentation\SAP\SHP633-302 SAP Final

1.0_17Apr2019.docx

Template No: CS_TP_BS016 Revision 4

Effective Date: 01Apr2016

Author:

Version Number: Version Date:

Reference: CS_WI_BS005

Final 1.0

17Apr2019

- Prescribed weekly PN/IV volume
- Prescribed weekly PN/IV calories
- Prescribed number of days per week of PN/IV
- Prescribed average number of hours per day of PN/IV
- Prescribed weekly EN volume
- Prescribed weekly EN calories

The following Gastrointestinal Symptoms History collected at the Baseline visit will be summarized for the ITT and Safety populations based on categories of not present, mild, moderate, and severe, with clinical significance also summarized where the event is present:

- Abdominal/belly pain
- Nausea/feeling queasy
- Vomiting/throw up
- Heartburn/reflux/spit up
- Gas/bloating
- Diarrhea/loose stool
- Constipation/very hard stool

Partial dates for the date of diagnosis of SBS and start of PN/EN dependency will use the first day of the month if only the day is missing. If both the day and month are missing, the first day of January will be used.

Medical and surgical history will be coded using the Medical Dictionary for Regulatory Activities (MedDRA). Investigator verbatim as well as preferred terms and system organ class will be included in the listings. The medical and surgical history will be summarized by system organ class (SOC) and preferred term (PT) within system organ class for the Safety population, with SOC sorted alphabetically and PT within SOC by descending incidence.

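### Section 9.1 imputes partial SBS-diagnosis and PN/EN start dates to the earliest possible day with no floor at birth, so an infant's reported duration can exceed the infant's age

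*SAP*

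**What the plan says.** For the date of SBS diagnosis and the start of PN/EN dependency, Section 9.1 of the SAP "will use the first day of the month if only the day is missing". It then adds: "If both the day and month are missing, the first day of January will be used". Neither sentence sets a lower bound, and none appears elsewhere in the SAP.

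The completed dates feed three infant durations in the same section:

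- SBS: "duration of SBS in months will be calculated as (Date of informed consent form signed – Date of diagnosis of SBS +1) / (365.25/12").
- PN/IV: "months since start of PN/IV dependency will be calculated as (Date of informed consent form signed – Start date of PN/IV dependency +1)/ (365.25/12").
- EN: "Years and months since start of EN dependency will be calculated in a similar manner but using the start date of EN dependency".

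All are rounded to 1 decimal. The same section also reports "Chronological (actual) age at informed consent date in months for the infant cohort", so age and duration share a reference date and a unit.

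Two other places bear on the point. Section 13.4 uses date of birth to calculate age for the Z-scores, so that date is available to the programmers. Section 6.3 says that nothing is imputed except partial dates for adverse events and prior or concomitant medications, which does not allow for the imputation in Section 9.1.

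**The concern.** The rule always picks the earliest day compatible with what was recorded. For an older patient this costs some accuracy. For an infant, the earliest day of the birth month or birth year usually lies before birth, so the resulting duration is impossible and not merely imprecise.

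The durations describe how long the treated infants have had SBS and depended on parenteral and enteral support. Section 5 of the PK analysis plan gives a minimum of 2 subjects for the infant cohort. In a cohort near that size, one such value would set the maximum and pull the mean visibly. Because chronological age at consent is summarised alongside, the report could show a longest disease duration greater than the oldest infant's age.

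**Working it through.** The SAP states no figure on this point, so there is none to reproduce. The check applies its own formula. All calendar dates below are assumptions.

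**Formula (Section 9.1).** Duration in months = (consent − event date + 1) / (365.25/12), with 365.25/12 = 30.4375. For comparison, age is taken as (consent − birth) / 30.4375; the SAP gives no explicit formula for age in months.

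**Main example.** Born 15 Oct 2018, consent 15 Apr 2019, PN start recorded only as 2018.

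- Imputed start 1 Jan 2018: (469 + 1)/30.4375 = 470/30.4375 = 15.4 months.
- Latest start that avoids a date before birth taken to its limit, PN from the day of birth: (182 + 1)/30.4375 = 183/30.4375 = 6.0 months. This is the largest possible duration.
- Excess: (470 − 183)/30.4375 = 287/30.4375 = 9.4 months.
- Effect on the mean of 2 infants: 9.4/2 = 4.7 months.

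**Largest possible excess over the duration counted from birth.**

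- Day missing, recorded month is the birth month: at most 30 days (born on the 31st), 30/30.4375 = 1.0 month.
- Day and month missing, recorded year is the birth year: at most 364 days (born 31 December of a non-leap year), 364/30.4375 = 12.0 months.

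**Further assumed infants, each diagnosed 5 days after birth (months).**

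| Born | Consent | Age | True duration | Day missing | Day and month missing |
|---|---|---|---|---|---|
| 20 Jun 2018 | 20 Dec 2018 | 6.0 | 5.9 | 6.7 | 11.6 |
| 15 Sep 2018 | 15 Mar 2019 | 5.9 | 5.8 | 6.4 | 14.4 |
| 20 Nov 2018 | 20 May 2019 | 5.9 | 5.8 | 6.6 | 16.6 |

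**A case with no violation.** Born 20 Nov 2018, diagnosed 25 Jan 2019, consent 20 Jul 2019. Both rules give 1 Jan 2019, so duration = 201/30.4375 = 6.6 months against an age of 8.0.

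**How the result depends on the time from birth to event.** All 365 birth dates in 2018 were run at assumed lags. The table gives the share of birth dates for which the imputed date precedes birth, provided the date is partial in the way shown.

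| Lag (days) | Day missing | Day and month missing |
|---|---|---|
| 0 | 96.7% | 99.7% |
| 7 | 73.7% | 97.8% |
| 30 | 0% | 91.5% |
| 60 | 0% | 83.3% |
| 90 | 0% | 75.1% |

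**With a floor at birth.** For the infant born 20 Nov 2018, the 6.6 and the 16.6 both become 182/30.4375 = 6.0 months, against an age of 181/30.4375 = 5.9. The remaining 0.1 comes from the added day and rounding.

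**Older cohort.** A child born 20 Nov 2010, consent 20 Nov 2018, with only 2010 recorded gets 8.9 years at age 8.0. The fault is the same but the relative error is smaller.

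**The case against.** The strongest reply is that this is an edge case. It needs a partial date, and that date must carry the birth month or birth year. For an infant within the first year or so of life the start of PN is recent, and a record with no month may be rare or may be queried. Section 5 leaves data validation and discrepancy handling to a Data Management Plan that is not at hand. The durations enter no endpoint or population definition. The SAP plans no covariate adjustment and no subgroup analyses. Minimum, maximum and age are reported, so an impossible value would be noticed.

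All of that stands, and it limits the weight of the point. It does not rescue the rule: followed as written, it produces an impossible number in the cases described.

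Some stronger readings are tempting but unsupported:

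- **That infants will generally or often get impossible durations.** The SAP gives no frequency of partial dates. It lists causes of SBS, among them intestinal atresia and gastroschisis but also trauma, cancer and Crohn's disease, and it does not state their timing. The percentages above hold only at the assumed lags.
- **That 4.7 months is a ceiling.** It belongs to one example. At the 12.0-month extreme, a mean of 2 would move by 12.0/2 = 6.0 months. Two is also a planned minimum, not the known cohort size.
- **That Section 6.3 has the safeguard missing here.** Its bounding step stops an imputed start date from falling after a complete stop date. That is an upper bound, and those dates have no floor at birth either.
- **That a cap at the consent date is also needed.** The rule moves dates earlier, so it cannot push one past consent unless the recorded month or year is already later than consent.

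**Conclusion.** The point holds in conditional form. Section 9.1 sets a rule that can place SBS diagnosis or PN/EN start before birth and so report a duration longer than the infant's life. This happens when a partial date carries the birth month or birth year and the infant was not born on the first day of that period. The excess is bounded by about 1 month in the first case and about 12 months in the second. The 15.4 against 6.0 months, and the 4.7-month shift in the mean, rest on assumed dates and on a cohort of 2. How often it would occur cannot be judged from the SAP.

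Only descriptive baseline characteristics are touched; no efficacy or safety result depends on these durations. The rule is wrong as written, with low severity, and is worth correcting because the correction is so small.

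**What to change.** Add to the partial-date paragraph of Section 9.1: *If the imputed date is before the date of birth, use the date of birth.* Apply it to both cohorts. No consent-date cap is needed.

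In Section 6.3, add the Section 9.1 history dates to the stated exceptions to the no-imputation rule, so that the two sections agree.

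The cost is one new sentence, one amended sentence and a one-line change to the derivation. No new data are required, since date of birth is already used in Section 13.4.

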10. MEASUREMENTS OF TREATMENT COMPLIANCE

Percent compliance will be calculated as 100 times the number of days the study treatment was administered per instructions by the number of days on treatment. Number of days on treatment is calculated as (last dose date – first dose date +1). The information whether the study treatment was administered per instructions is captured on the study drug administration daily diary. Administration of the study treatment by the investigator will be considered per instructions. Subjects will be considered compliant overall for study medication if the calculated compliance is \geq 80%. Overall treatment compliance will be presented for both percent compliance calculations using descriptive statistics and the number and percentage of

Document: T:\Shire\Teduglutide\XXA39799\Biostatistics\Documentation\SAP\SHP633-302 SAP Final

1.0_17Apr2019.docx

Template No: CS_TP_BS016 Revision 4

Effective Date: 01Apr2016

Author:

Version Date: 17Apr2019

Version Number:

Reference: CS_WI_BS005

Final 1.0

subjects who are ≥ 80% compliant for the ITT and Safety populations. Treatment compliance by visit will not be calculated.

11. EFFICACY/PHARMACODYNAMIC EVALUATION

11.1. Analysis of Efficacy and Pharmacodynamic Variables

Primary efficacy/pharmacodynamic analyses will be conducted on the ITT population. The PP population will be used for sensitivity analysis purpose.

PN/IV and EN support will be reported in both subject diary data and the investigator-prescribed data in the eCRF. Diary and prescribed PN/IV and EN volume/calories will be normalized to weight in order to facilitate comparability of results across patients in this pediatric population. Data will be summarized at all scheduled visits during the 24-week treatment period and the follow-up period (Week 25, 26, 27, 28). An End of Treatment (EOT) time point will also be added. Data collected at unscheduled time points will be included in the listings but will not be summarized at those unscheduled time points.

Prescribed data are the most recent PN/IV or EN prescription (from either baseline or prescription adjustments) prior to or on the date of visit, captured in the PN/IV or EN history and PN/IV or EN adjustments eCRFs.

Average daily values normalized to weight will be calculated for PN/IV volume, PN/IV calories, EN volume and EN calories as follows:

Average Prescribed daily value = (prescribed weekly value / 7) / last available body weight prior to or on the date of visit

Calculation of post-baseline diary PN/IV and EN parameters (including hours per day and days per week of PN/IV support) will be based on the daily support recorded in subjects' diaries within 7 days prior to the date of each scheduled post-baseline visit. Baseline diary PN/IV and EN parameters will be calculated using the most recent 14 days of diary data collected prior to the first dose, and week 1 calculations will not use any pre-baseline diary data.

Average daily values normalized to weight will be calculated for PN/IV volume, PN/IV calories, EN volume and EN calories as follows:

Average diary daily value = (sum of non-missing daily values in the diary / number of days with non-missing values) / last available body weight prior to the visit

If more than 2 days' values in a week are missing, the average daily value will not be calculated and will be assigned as missing. If more than 5 days' values in two weeks before baseline visit, the baseline values are missing. These missing data handling rules will be used to calculate all other diary average diary parameters, including PN/IV calories, PN/IV hours per day, PN/IV days per week, EN volume, and EN calories.

Document: T:\Shire\Teduglutide\XXA39799\Biostatistics\Documentation\SAP\SHP633-302 SAP Final

__1.0__17Apr2019.docx

Version Number: Version Date: Final 1.0 17Apr2019

Author:

Template No: CS_TP_BS016 Revision 4

Effective Date: 01Apr2016

Reference: CS_WI_BS005

Percent reduction in weight-normalized diary and prescribed PN/IV volume from baseline at the scheduled visit will be calculated using the formula below:

% reduction in PN/IV volume at the visit = [(average daily value at the scheduled visit - average daily value at baseline) / average daily value at baseline] * 100

Percent reduction calculation will be performed on both diary and prescribed PN/IV volume data.

Change and percent change from baseline in PN/IV and EN support

The absolute and percent change from baseline in average daily values for PN/IV and EN support (volume and calories) to each scheduled visit during the 24-week treatment period, as well as at EOT and the follow-up period (Week 25, 26, 27, 28), will be presented using descriptive statistics defined in Section 6.1. For EN summary, change from baseline will only be calculated for subjects who took any EN at baseline.

Mean ± SE plots of percent change in PN/IV and EN support (volume and caloric intake) will be generated.

Plots of PN/IV and EN support (volume and caloric intake) by visit will be presented for each individual subject in the ITT population.

95% confidence intervals of the mean will be generated for Week 20 and Week 24/EOT.

Change and percent change from baseline in citrulline

The absolute and percent change in citrulline from baseline to each scheduled visit during the 24-week treatment period, as well as at EOT and the follow-up period (Week 28), will be presented using descriptive statistics defined in Section 6.1 for the cohort of children 1-15 years of age.

≥ 20% Reduction in PN/IV volume at each study visit

PN/IV volume reduction at each study visit compared to baseline will be calculated using average daily values. The number and percentage of subjects who achieve at least a 20% reduction in PN/IV volume will be presented at each scheduled visit during the 24-week treatment period, as well as at EOT and the follow-up period (Week 25, 26, 27, 28).

Complete weaning off PN/IV support at EOT

A subject will be considered to have achieved independence from PN/IV support (completely weaned off PN/IV) if the investigator prescribes no PN/IV (volume and calories) and there is no use of PN/IV (volume and calories) recorded in the subject diary during the 7 days prior to EOT. The number and percentage of subjects who completely wean off PN/IV support up to EOT will be presented. A listing will present the study week when complete wean off was first achieved for these subjects who completely wean off PN/IV support at EOT.

Change and percent change from EOT in PN/IV support, citrulline, EN support at EOS

Document: T:\Shire\Teduglutide\XXA39799\Biostatistics\Documentation\SAP\SHP633-302 SAP Final

1.0_17Apr2019.docx

Version Number: Final 1.0 Version Date: 17Apr2019

Reference: CS WI BS005

Template No: CS_TP_BS016 Revision 4

Effective Date: 01Apr2016

Author:

Copyright © IQVIA. All rights reserved.

The absolute and percent change from EOT to EOS in average daily values for PN/IV and EN support (volume and calories) as well as citrulline (only for the cohort of children 1-15 years age) will be presented using descriptive statistics defined in Section 6.1. If subject has weaned-off PN/IV or EN at EOT, change from EOT for those parameters will not be calculated.

Change and percent change from baseline in hours per day and days per week of PN/IV support

Change and percent change from baseline in hours per day and days per week of PN/IV support to each visit during 24-week treatment period, as well as at EOT and the follow-up period (Week 25, 26, 27, 28), will be presented using descriptive statistics defined in Section 6.1.

Hours per day of diary PN/IV support for all visits except the baseline visit will be calculated as follows:

Hours per day of diary PN/IV support = (sum of hours per day for each day that PN/IV intake data is recorded within the 7 days prior to the visit / number of days that PN/IV hours per day data is recorded within the 7 days prior to the visit)

Prescribed PN/IV hours per day for each visit (including baseline) will be taken from the most recent prescription data prior to or at that visit.

Days per week of diary PN/IV support for all visits except the baseline visit will be calculated as follows:

Days per week of diary PN/IV support = (number of days with non-zero values for PN/IV volume within the 7 days prior to the visit / number of days for which any PN/IV intake data is recorded within the 7 days prior to the visit) * 7

For the week 1 visit, data prior to the baseline visit will not be used for the calculation.

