2.2.1. EFFICACY/PHARMACODYNAMIC ASSESSMENTS

The efficacy/pharmacodynamic endpoints include:

- Change (absolute and percent change) from baseline in PN/IV support (volume and calories), citrulline (only for the cohort of children 1-15 years of age), and enteral nutritional support (volume and calories), separately, at each visit
- Reduction in PN/IV volume of at least 20% at week 24 (or EOT) compared to baseline
- 100% reduction in PN/IV volume (complete weaning of PN/IV support) at week 24 (or EOT) compared to baseline
- ≥20% reduction in PN/IV volume at each visit
- Change (absolute and percent change) from week 24 (or EOT) in PN/IV support (volume and calories), citrulline (only for the cohort of children 1-15 years of age), and enteral nutritional support (volume and calories), separately, to week 28 (or EOS)
- Change in hours per day and days per week of PN/IV support

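### The formula labelled percent reduction in PN/IV volume is a percent change, so its sign runs against the ≥20% reduction endpoints that depend on it

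*SAP*

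**What the plan says.** SAP Section 11.1 introduces the derivation with "Percent reduction in weight-normalized diary and prescribed PN/IV volume from baseline at the scheduled visit will be calculated using the formula below". The formula that follows sets the percent reduction at the visit equal to an expression that reads, after its opening brackets, "average daily value at the scheduled visit - average daily value at baseline) / average daily value at baseline] * 100". A further sentence applies it to both the diary and the prescribed volumes.

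The endpoints that need a percent reduction are stated in words:

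- Section 2.2.1: "Reduction in PN/IV volume of at least 20% at week 24 (or EOT) compared to baseline", together with the same threshold at each visit.
- Section 11.1, under the heading for the ≥20% reduction: "The number and percentage of subjects who achieve at least a 20% reduction in PN/IV volume will be presented at each scheduled visit". The same sentence extends the counts to EOT and to Weeks 25 to 28. The text there adds only that average daily values are used, and these are the inputs to the formula above.

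Section 2.2.1 also lists "100% reduction in PN/IV volume (complete weaning of PN/IV support) at week 24 (or EOT) compared to baseline". Section 11.1 derives complete weaning separately: a subject qualifies "if the investigator prescribes no PN/IV (volume and calories) and there is no use of PN/IV (volume and calories) recorded in the subject diary" over the 7 days before EOT.

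**The concern.** Label and formula disagree in sign. Visit minus baseline, divided by baseline, is the usual percent change: a fall gives a negative number and a rise a positive one. A quantity called percent reduction, compared with a threshold of at least 20, has to be positive when volume falls. Section 11.1 has its own heading for change and percent change from baseline, so the SAP treats the two as separate quantities, yet it puts the percent-change expression under the reduction label.

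At stake are the counts and percentages of subjects with a ≥20% reduction, at every scheduled visit, at week 24/EOT and during follow-up, for both data sources. Section 6.1 confines the study to descriptive statistics, so such counts are part of how efficacy will be read. The cohorts are small: Section 5 of the PK analysis plan gives planned minimums of 5 children and 2 infants. At those minimums one misclassified subject moves a cohort's responder percentage by 1/5 = 20 or 1/2 = 50 percentage points.

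**Working it through.** The SAP states no numeric result on this point, so there is no figure to reproduce. The check is to evaluate the formula as written and compare it with the threshold.

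**Inputs**
- Formula as written (Section 11.1): W = (visit − baseline) / baseline × 100.
- Formula matching the label: R = (baseline − visit) / baseline × 100 = −W.
- Responder rule (Sections 2.2.1 and 11.1): at least 20.
- Baseline of 60 mL/kg/day: an assumption for illustration, not in the SAP. W and R depend only on visit/baseline, so any positive baseline gives the same percentages for the same ratio.

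**Examples**
- 60 to 42: W = (42 − 60)/60 × 100 = −30; R = +30.
- 60 to 78: W = (78 − 60)/60 × 100 = +30; R = −30.

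**Range of visit values**

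| Visit value | W (as written) | W ≥ 20? | R (sign corrected) | R ≥ 20? |
|---|---|---|---|---|
| 0 | −100 | no | +100 | yes |
| 30 | −50 | no | +50 | yes |
| 48 | −20 | no | +20 | yes |
| 54 | −10 | no | +10 | no |
| 60 | 0 | no | 0 | no |
| 66 | +10 | no | −10 | no |
| 72 | +20 | yes | −20 | no |
| 90 | +50 | yes | −50 | no |
| 120 | +100 | yes | −100 | no |

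The two rules disagree whenever volume falls by 20% or more (a true responder, missed) and whenever it rises by 20% or more (wrongly counted). Between those limits both give non-responder.

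**What else uses the expression**
- Percent change from baseline, its mean plots and its confidence intervals: visit minus baseline over baseline is the ordinary definition, so these are right as they stand.
- Complete weaning: decided by zero prescription and zero diary use, with no percentage involved, so the sign cannot affect it.

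**The case against.** The best defence is that nobody could mistake the intent. The endpoints are written in words as reductions, and Section 2.2.1 equates a 100% reduction with complete weaning, which fixes a fall as the positive direction. Literal coding would report children whose support rose as having a reduction, and would place a fully weaned child below 20%. That would clash visibly with the percent-change tables, the weaning table and the individual subject plots. A programmer would probably notice, and the table shells, held in a separate file (Section 16.1), may already have it right. This stands as an argument about likelihood. It does not make the written rule correct, and nothing in the SAP shows that the slip was caught.

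Three stronger readings are tempting, and the SAP supports none of them:

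- **That the 100% reduction endpoint is inverted too.** A visit value of 0 does give −100, but Section 11.1 does not derive complete weaning from this formula.
- **That every responder classification is reversed.** Subjects whose volume stays within 20% of baseline in either direction are non-responders under both signs.
- **That the main efficacy result is inverted.** Section 2.2.1 lists several efficacy endpoints and ranks none as the main one. The change and percent-change summaries, complete weaning, and the hours-per-day and days-per-week analyses are untouched.

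**Conclusion.** The point holds for the ≥20% reduction endpoints and no further. As written, the SAP's only numeric formula for them carries the wrong sign: every subject with a fall of 20% or more would be missed, and every subject with a rise of 20% or more would be counted. This covers each scheduled visit, week 24/EOT and Weeks 25 to 28, for diary and prescribed volumes alike. The conclusion rests on reading the formula together with the stated threshold and needs no assumption about the data; the baseline of 60 is only an illustration. Whether a wrong table would actually result depends on programming that is not at hand. The intended direction is clear, so this is a specification error to correct and not evidence that results will be misreported.

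**What to change.** In Section 11.1 make one of two changes:

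1. Define percent reduction, in average daily values, as (baseline − visit) / baseline × 100, with a responder at ≥20. Keep the present expression as well, labelled percent change from baseline, because the percent-change summaries use it.
2. Or keep the present expression, relabel it percent change from baseline, and define a responder as ≤ −20.

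Then check the programming specification and the table shells against the chosen wording. Leave the definition of complete weaning as it is. Adding a rule that a computed reduction of 100 counts as complete would create a second definition: a subject could reach 100 on diary volume alone and still fail the existing rule, which requires both the prescription and the diary to show no volume and no calories.

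The cost is one line of SAP text and a short programming check. No data collection, sample size or analysis method changes.
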